6.3 Analysis Populations

6.3.1 Intent-to-Treat (ITT) Population

The ITT population includes all subjects who were enrolled and treated with the NanoKnife System. Any subject who has a NanoKnife probe inserted will be considered treated for the ITT population. Note: Subjects who are enrolled but not treated will be documented as screen failures. The ITT population will serve as the primary analysis set for all safety and efficacy endpoints.

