5. ADVERSE EVENTS DEFINITIONS AND REPORTING

5.1 Adverse Events

An adverse event (AE) is defined as any untoward medical occurrence, unintended disease or injury or any untoward clinical signs in subjects whether or not related to the Investigational Product and includes events related to the procedures involved. Safety events will refer to all adverse events (AEs), serious AEs (SAEs), adverse device effects (ADEs), and unanticipated adverse device effect (UADEs). This definition does not imply a relationship between the adverse event and the study procedure. The principal investigator will determine AE relationship (choices will be listed on the AE eCRF).

Any relevant medical conditions, problems, signs, symptoms and findings occurring prior to treatment are to be reported as pre-existing conditions and documented on the Medical History eCRF. If a pre-existing condition worsens during the follow-up (frequency increases and/or severity grade increases), it should be documented as an AE.

At each evaluation from the time of enrollment, the investigator or designee will determine whether an AE has occurred. The AE, date of onset, seriousness, severity, duration, treatment, outcome and relationship will be recorded on the AE eCRF. Adverse events will be assessed by a physician and monitored until they are resolved, stabilized, or the subject has reached study completion.

The term "severity" refers to the intensity of a specific event (CTCAE v5.0 will be used to determine this). The seriousness (not severity) serves as a guide for defining regulatory reporting obligations.

All adverse events will be reported by the investigator and/or study team and reviewed by the sponsor in compliance with applicable regulations. Adverse events may be volunteered by subjects, elicited by the investigator or designee, or collected via observation by the investigator.

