8.7 Medical Risk Analysis

Because the NanoKnife System is investigational within the prostate there may be potential risks and side effects that are unknown at this time. A clinical risk analysis has been prepared which describes the hazards associated with the use of the device and the associated clinical risks associated with the procedure (e.g., general anesthesia) along with the mitigations available to reduce this hazard. Potential risks associated with the use of the NanoKnife System include, but are not limited to, the risk outlined in *Table 8-1*.

Table 8-1: Potential Hazards

Hazard	Potential Effect(s)	Early Recognition	Mitigation
General anesthesia (procedural)	Aspiration-infection Pulmonary compromise-ARDS Urinary retention, suprapubic catheterization Paralysis Coma Death	Periodic assessment of airway patency, respiratory rate, and oxygen saturation. Routine monitoring of vital signs	Supervision by trained anesthesiologist Intra-operative monitoring Pre-op history and physical exam
Muscle Blockade (procedural)	Extended anesthesia (too much blockade) Insufficient anesthesia—pain Toxicity (If the organ that metabolizes the muscle block has compromised function)	Physical assessment and pharmacological management per ASA Standards	Pre-op history and physical exam Selection of appropriate agents. Patient management by Anesthesiologist.
Cardiac Arrhythmia (both procedural and device, unlikely from device due to distance)	Acute decrease in BP Fibrillation Cardioversion Death	The Anesthesiologist will be monitoring the patient continuously during procedure.	Anesthesia monitoring History and physical exam Availability of treatment drugs and cardioversion equipment; ECG monitoring and procedure pacing
Multiple Prostate Biopsies (procedural)	Bleeding Infection Hematoma Pain	Needle placement is performed using continuous image guidance.	Biopsy technique and physician training
IRE electrode needles placed in or through sensitive structures. (Foreseeable misuse)	Sharp trauma / perforation of structures. (Blood vessels, nerves, urethra, bowel, bladder). Bleeding Infection. Pain	Probe placement is performed using continuous image guidance. Patients will be monitored for hemodynamic instability	Physician training; product labeling

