12.8 Safety Analyses

All safety analyses will be presented for the ITT population. If a subject is re-treated with something other than the NanoKnife System during the study, the subject should exit the study; any safety data collected during and after the re-treatment will not be included in the safety analyses. Further, if a lesion is re-treated with the NanoKnife System more than once during the study, the subject should exit the study; any safety data collected for a subject after the second re-treatment of the same lesion will not be included in the safety analyses.

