12.8.2 Deaths and Serious Adverse Events

Serious adverse events (SAEs) and NanoKnife System treatment-related SAEs will be summarized separately by body system and preferred term for the ITT subjects. All SAEs recorded on the CRF will be provided in a listing for subjects in the ITT population.

A table presenting the number of events and the number and percentage of subjects by body system and preferred term who experienced SAEs related to NanoKnife System treatment during the study will be presented for the ITT population. UADEs and deaths occurring in the study will also be listed for all subjects in the ITT population.

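### Safety is counted only from the first electrode probe, so harm after the procedure starts but before a probe is placed falls outside the primary safety result

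*Combined protocol and SAP*

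**What the plan says.** Enrollment happens at consent (Protocol 4.2). Entry to the analysis comes later. Protocol 6.3.1 states: "Any subject who has a NanoKnife probe inserted will be considered treated for the ITT population". It then says "Subjects who are enrolled but not treated will be documented as screen failures", and gives this set its role: "The ITT population will serve as the primary analysis set for all safety and efficacy endpoints". SAP 9.3.2 repeats the probe rule and the role. SAP 12.8 adds: "All safety analyses will be presented for the ITT population". SAP 12.8.2 limits the SAE listing to ITT and says "UADEs and deaths occurring in the study will also be listed for all subjects in the ITT population". The only wider set, the Screening Set in SAP 9.3.1, serves only to report the analysis sets.

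The study procedure in Protocol 4.6 begins before any electrode probe is placed. It includes general anesthesia, a Foley catheter, an intravenous antibiotic and a transrectal ultrasound device. Table 8-1 lists general anesthesia as a procedural hazard, with potential effects up to coma and death. The primary safety objective (3.3.1) covers the procedure as well as the period after it.

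On recording, Protocol 5.1 says in one paragraph that "problems, signs, symptoms and findings occurring prior to treatment are to be reported as pre-existing conditions", to be entered as medical history. The next paragraph says: "At each evaluation from the time of enrollment, the investigator or designee will determine whether an AE has occurred". Table 4-4 marks adverse event assessment from Visit 3 (the treatment visit) onward, and not at Screening or Baseline.

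**The concern.** Membership of the safety set depends on getting through the first part of the procedure whose safety is being measured. If a man aspirates or arrests after induction and the case is abandoned before a probe goes in, he becomes a screen failure because of the harm itself. Any resulting bias can only favour the device.

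The conflict in 5.1 is a second, separate problem. Two sites could classify the same event between consent and treatment differently, one as medical history and the other as an adverse event.

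**Working it through.** **Who is counted.** Applying Protocol 6.3.1 and SAP 9.3.2, 12.8 and 12.8.2 to three cases:

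| Case | Status | Safety tables | SAE, death and UADE listings |
|---|---|---|---|
| Harm after induction; stopped before the first electrode probe | Enrolled, not treated: screen failure | Out | Out |
| Harm after induction, before the first probe; procedure continues | ITT | In, if recorded as an adverse event | In, if recorded as an adverse event |
| Harm after the first probe; stopped at any later point | ITT | In | In |

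Only the first row is lost through the population rule. Neuromuscular blockade is given after probe placement (Protocol 4.6.3), so events from blockade or pulsing belong to the third row. Protocol 6.5 keeps subjects whose treatment was cut short by adverse events, but only those undergoing treatment, and 6.3.1 ties treatment to an inserted probe. It therefore does not bring the first row back.

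**The plan's own safety figures (Protocol 6.2).** Inputs: true event rate 1.6%, n = 100, drop-out 15%.
- Probability of at least one event: 1 − (1 − 0.016)^100 = 0.8007, which matches the stated figure of more than 80%.
- Inflation: 100 / (1 − 0.15) = 117.6, rounded up to 118, as stated.

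This arithmetic is not in dispute. The question is which subjects are counted.

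**Illustration of size.** The documents give no rate of abandoned cases or of pre-probe events. Assume 118 probed subjects with no event of a given type, and k further enrolled subjects, k = 0, 1 or 2, who have such an event after induction and are never probed. The intervals are exact (Clopper-Pearson, the method the SAP uses for the biopsy rate). For x events in n, the limits are the 2.5% point of Beta(x, n − x + 1) and the 97.5% point of Beta(x + 1, n − x); the lower limit is 0 when x = 0. For 0/118 the upper limit is 1 − 0.025^(1/118) = 3.08%.

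| Pre-probe events k | Reported under the plan | Counting everyone whose procedure started |
|---|---|---|
| 0 | 0/118 = 0% (0 to 3.1%) | 0/118 = 0% (0 to 3.1%) |
| 1 | 0/118 = 0% (0 to 3.1%) | 1/119 = 0.8% (0.02 to 4.6%) |
| 2 | 0/118 = 0% (0 to 3.1%) | 2/120 = 1.7% (0.2 to 5.9%) |

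The reported result is the same in every row, so the tables could not tell these situations apart.

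**Recording rules in 5.1.** One rule turns on treatment, the other on enrollment, which is consent. Between the two, both apply and they give different answers. Table 4-4 does not settle it: it has an assessment at Visit 3 but none between consent and that visit.

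**The case against.** A safety set of treated subjects is a visible and deliberate choice, and much of the risk lies inside it. Hazards from electrode placement, blockade and pulsing all arise once a probe is in. A reader might infer that the rule removes every procedure aborted for harm. It does not, because a case aborted after the first probe stays in ITT.

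A reader might also infer that the event disappears altogether. The documents do not support that. Protocol 6.1 promises data for all enrolled subjects and by-subject adverse event listings. SAP 12.8.1 has a listing of all adverse events on the CRF that names no population. The date-imputation table in SAP 10.6.1, which covers adverse events and concomitant medication, has rows for untreated patients. Site reporting of SAEs and deaths (Protocol 5.2 and 5.5) is not limited to ITT. These points stand, but they do not put the subject into the primary endpoint or the ITT-limited listings. The general listing also sits under SAP 12.8, whose opening sentence restricts safety analyses to ITT.

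A third tempting reading is that 5.1 sends everything before treatment to medical history. That is one of two conflicting rules. An anesthetic event is not naturally a pre-existing condition, the adverse event definition includes events related to the procedures involved, and assessment is scheduled at Visit 3. The probe definition in 6.3.1 is also given for ITT, not for adverse event collection. What stands is a contradiction to reconcile.

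Finally, UADEs add little here, because a UADE must be associated with the device and no probe is yet in place.

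**Conclusion.** The point holds in a limited form. Followed as written, the plan leaves a death or SAE that occurs between the start of the procedure and the first electrode probe, in a case then abandoned, out of the primary safety endpoint, the safety tables and the SAP 12.8.2 listings. The direction of any bias favours the device. Whether a general listing would show the event is unclear.

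The size cannot be estimated from the documents. The figures of 0/118 against 1/119 or 2/120 assume one or two such cases and no like event among 118 probed men. The true number may be zero, and the intervals overlap widely. A reader might set 1.7% against the 1.6% in Protocol 6.2 and conclude that a detectable rate had been hidden. That does not follow: 1.6% is a true rate at which 100 subjects give about an 80% chance of seeing at least one event, not a threshold for an observed proportion.

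The contradiction in 5.1 stands on the text alone and needs no assumption. Both matters are worth correcting because the correction is cheap.

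**What to change.** - Add a Safety Set to Protocol 6.3 and SAP 9.3: all enrolled subjects in whom the Visit 3 procedure is started, from anesthesia induction, whether or not a probe is inserted. Use it for Protocol 6.8 and SAP 12.8, and change the sentences that make ITT the safety set. Keep the probe rule for the efficacy ITT set.
- In SAP 12.8.2, list deaths and SAEs, and any UADEs, for all enrolled subjects. This also covers events between consent and induction, such as those linked to bowel preparation, which the Safety Set would not include.
- Reconcile the two rules in Protocol 5.1 on when adverse event recording begins, and align Table 4-4 (and SAP Table 1) with the result.

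The cost is protocol and SAP wording and one population flag. The safety denominator may exceed the efficacy denominator by a few subjects. If adverse events are collected from consent, more unrelated events will be recorded.

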6.3.2 Per Protocol (PP) Population

The PP population includes all subjects who were enrolled and treated with the NanoKnife System, and who had no major protocol deviations. The PP population will serve as a supportive analysis set for all efficacy endpoints.

6.4 Missing Data

The following imputation methods will be used for the primary analysis of all endpoints:

- When calculating the proportion of subjects with a negative in-field biopsy, subjects with missing biopsy information post-ablation will be imputed as “positive”
- Subjects with missing pre- or post-ablation prostate volume measurements will be imputed as having a zero change in volume
- Missing PSA data will be imputed using last observation carried forward (LOCF)
- Missing data for IIEF-5, IPSS and EPIC questionnaires will be imputed using a multiple imputation approach at the item/question level.

All other endpoints/data (e.g., safety events) will be analyzed based on available (non-imputed) data, unless specified otherwise.

6.5 Subject Disposition

All subjects undergoing treatment as part of this study will be included in analyses, including those subjects for which treatment could not be completed due to adverse events or other complicating factors. Subjects will be followed for a maximum of 12 months, unless a subject has unresolved AEs, in which case they will be followed until all AEs are resolved or are determined to have no resolution, and disposition of all these subjects will be presented, including those completing follow-up and those

excluded due to treatment failure, adverse events, withdrawal by the subjects or Investigator, and those lost to follow-up.

6.6 Pooling

All tabulations will pool data across study sites. However, as stated above, data listing will be presented by individual study site.

6.7 Primary Effectiveness Endpoint

The primary efficacy endpoint is the rate of subjects with a negative in-field biopsy at 12 months. The number and proportion of subjects obtaining a negative in-field biopsy at 12 months will be presented, along with the 95% confidence interval of the proportion.

Subjects who are biopsied prior to 12 months (if there are positive findings on the 3-month mpMRI, if the subject is deemed to have biochemical progression, or if the treating physician deems there to be clinical suspicion) and have a positive in-field biopsy will be imputed as failures for the analysis of the primary efficacy endpoint. Note: Subjects with early positive out-of-field biopsies will not be considered failures for the primary efficacy endpoint.

6.8 Primary Safety Endpoint

The primary safety endpoint is the incidence of adverse events by type and CTCAE v5.0 severity through 12 months. The number and proportion of subjects who experienced at least one adverse event will be summarized, and the 95% confidence interval of the proportion will be presented.

If a subject is re-treated with something other than the NanoKnife System during the study, safety data collected during and after the re-treatment will not be included in the safety analyses.

6.9 Secondary Endpoints

Additional endpoints for statistical consideration will include the following:

- Rate of negative in-field biopsy at 12 months as defined by the Delphi consensus criterion of absence of clinically significant disease (≤ 3 mm of Gleason ≤ 6 disease in any biopsy core is insignificant)¹
- Assessment of urinary function by comparison of pre- and post-operative UCLA Expanded Prostate Cancer Index Composite (UCLA-EPIC) Urinary Domain² and International Prostate Symptom Scores (IPSS)³ and IPSS Quality of Life (IPSS-QoL) scores.
- Assessment of erectile function by comparison of pre- and post-operative 15-Item International Index of Erectile Function (IIEF-15)⁴ potency scores.
- Effectiveness of therapy by measurement of prostate-specific antigen (PSA) kinetics including time to PSA nadir.
- Assessment of changes in prostate volume by comparison of pre-treatment and 12-month prostate volume measured via mpMRI.
- Assessment of ablation effectiveness by evaluation of prostate tissue by mpMRI at 3 months post-treatment and at 12 months post-treatment.

- Assessment of need for secondary or adjuvant treatment following treatment with the NanoKnife System.
- Evaluation of subject reported pre- and post-operative Quality of Life (QoL) using the 5-dimension scale EuroQol (EQ-5D®).⁵

If a subject is re-treated with something other than the NanoKnife System during the study, secondary endpoint data collected during and after the re-treatment will not be included in the secondary endpoint analyses.

Negative in-field biopsy at 12 months as defined by Delphi consensus criteria: Negative in-field biopsy is defined to be the absence of clinically significant disease (≤ 3 mm of Gleason ≤ 6 disease in any biopsy core is insignificant).¹ Prostate cancer that is ≤ 3 mm Gleason 6 will be considered clinically insignificant cancer and will not be considered a positive biopsy for this endpoint.

UCLA-EPIC²: The Urinary domain score from the UCLA-EPIC (University of California Los Angeles Expanded Prostate Cancer Index Composite) Urinary questionnaire will be presented for each visit (i.e., 1, 3, 6, 9, and 12 month follow-up). In addition, the 6-month and 12-month change from baseline will also be tabulated. See **Appendix E – Subject Questionnaires – 1.1 UCLA-EPIC** section for more details on the questionnaire and scoring instructions.

IPSS and IPSS-QoL³: The total score from the IPSS (International Prostate Symptom Score) and IPSS-QoL questionnaire will be presented for each visit (i.e., 1, 3, 6, 9, and 12 month follow-up). In addition, the 6-month and 12-month change from baseline will also be tabulated. See **Appendix E – Subject Questionnaires – 1.2 IPSS and IPSS-QoL** section for more details on the questionnaire and scoring instructions.

IIEF-15⁴: The IIEF-15 (International Index of Erectile Function 15 items) will have the Total Satisfaction Score and each of the 4 subscales (Erectile Function, Intercourse Satisfaction, Orgasmic Function, and Sexual Desire) will be presented for each visit (i.e., 1, 3, 6, 9, and 12 month follow-up). In addition, the 6-month and 12-month change from baseline will also be tabulated. See **Appendix E – Subject Questionnaires – 2.1 IIEF-15** section for more details on the questionnaire and scoring instructions.

PSA: The mean PSA levels at each visit, the overall percent reduction in PSA levels from baseline to each visit, and the proportion of subjects with a PSA reduction compared to baseline at each visit will be presented. Mean PSA nadir and post-nadir PSA values through 12 months post-treatment will be summarized.

Prostate Volume: The mean prostate volume at each visit, the overall percent reduction in prostate volume from baseline to each visit, and the proportion of subjects with reduction in prostate volume compared to baseline at each visit will be presented, as measured by mpMRI.

Evaluation of Prostate Tissue by mpMRI: The number and proportion of subjects determined to have cancer-bearing prostate tissue lesions on the 12-month mpMRI will be presented.

Secondary or Adjuvant Treatment: The number and proportion of subjects undergoing secondary or adjuvant treatment during the study will be presented.

EQ-5D⁵: The EQ-5D (EuroQoL – 5 Dimensions) will have the Total score and each of the 5 subscales (Mobility, Self-care, Usual activities, Pain/Discomfort, Anxiety/Depression) presented for each visit (i.e., 1, 3, 6, 9, and 12 month follow-up). In addition, the 6-month and 12-month change from baseline will also be tabulated. See **Appendix E – Subject Questionnaires – 3.1 EQ-5D** section for more details on the questionnaire and scoring instructions.

6.10 Exploratory Endpoint

Rate of progression, re-intervention, and adverse events: Once they complete 12-month follow-up, subjects will be referred to standard of care clinical follow up. AngioDynamics will be allowed to access EMR and similar medical records outside of the study through five years of follow up in order to assess long-term rate of progression, the need for re-intervention, and safety.

7 DATA HANDLING AND QUALITY ASSURANCE

7.1 Case Report Forms

This trial will utilize electronic Case Report Forms (eCRFs) to collect subject data via an electronic data capture (EDC) system. Case Report forms are presented in **Appendix B**.

The investigator is responsible for the accuracy and completeness of data reported on the eCRFs. Each set of eCRFs must be reviewed and signed by the investigator. The investigator also agrees to maintain accurate source documentation as part of the subject's medical records. These source documents may include chart notes, laboratory reports, images, etc. All eCRFs will be source data verified by the Clinical Research Associate (CRA) during regularly scheduled monitoring visits.

7.2 Subject Identifiers

All data used in the analysis and reporting of the study will be without identifiable reference to the subject. Only the unique subject number will be used to identify subject data submitted to the sponsor, and only the investigating site will be able to link the unique subject ID to the subject's name.

7.3 Study Monitoring Duties

Clinical site monitoring is conducted to ensure that the rights and well-being of trial participants are protected, that the reported trial data are accurate, complete and verifiable, and that the conduct of the trial is in compliance with the currently approved protocol/amendments (s), with International Conference on Harmonisation Good Clinical Practice (ICH GCP), and with applicable regulatory requirement(s).

Study monitors will conduct site initiation visits to train the study sites on the protocol prior to the study start. Interim monitoring visits will be conducted to check compliance with the protocol including completeness of informed consent forms and accuracy of entries on the eCRFs. Source documents will be verified where applicable. Study close-out visits will also be conducted per study monitoring plan, following all applicable regulatory requirements. Records of each visit will be documented in the appropriate monitoring report format and will include a statement of findings, conclusions, and any actions taken to correct any deficiencies noted during the visit. The monitor will report to the sponsor any non-compliance with the signed Investigator Statement, the study protocol, applicable GCP requirements, or any conditions imposed by the IRB. The frequency of monitoring visits will be determined by the sponsor.

The Sponsor or sponsor's designee, and the FDA may conduct site audits at any time during the study to ensure the validity and integrity of the data.

Quality control (QC) procedures will be implemented beginning with the data entry system and data QC checks that will be run on the database. Any missing data or data anomalies will be communicated to the site (s) for clarification/resolution.

Following written Standard Operating Procedures (SOPs), the monitors will verify that the clinical study is conducted and data are generated and documented, and reported in compliance with the protocol, ICH GCP, and applicable regulatory requirements.

The investigational site will provide direct access to all study related source data/documents, and reports for the purpose of monitoring and auditing by the sponsor, and inspection by local and regulatory requirements.

